13.5.	Protocol compliance.....	47
13.6.	Notification of Serious Breaches to GCP and/or the protocol	47
13.7.	Data protection and participant confidentiality	47
13.8.	Financial and other competing interests for the Chief Investigator, PIs at each site and committee members for the overall trial management.....	48
13.9.	Indemnity	48
13.10.	Amendments.....	49
13.11.	Post trial care.....	49
13.12.	Access to the final trial dataset	49
14.	Dissemination policy.....	49
14.1.	Authorship eligibility guidelines and any intended use of professional writers	49
15.	REFERENCES.....	51
16.	APPENDICES	57
16.1.	Appendix 1-Risk.....	57

16.2.	Appendix 2 - Trial management / responsibilities	61
16.3.	Appendix 3 – Authorisation of participating sites	62
16.4.	Appendix 4 – Schedule of Procedures	63
16.5.	Appendix 5 – Safety Reporting Flow Chart	63
16.6.	Appendix 6 – Amendment History	65

I. LIST OF ABBREVIATIONS

AE	Adverse Event
AR	Adverse Reaction
BEST	Bronchiectasis exacerbation and symptom tool
BIM	Bronchiectasis Impact Measure
bPIS	Brief Participant Information Sheet
CI	Chief Investigator
CNORIS	Clinical Negligence and Other Risks Insurance Scheme
COPD	Chronic Obstructive Pulmonary Disease
DMC	Data Monitoring Committee
ECG	Electrocardiogram
eCRF	Electronic Case Report Form
EDC	Electronic Data Capture
EMBARC	European Multicentre Bronchiectasis Audit and Research Collaboration
FDA	US Food & Drug Administration
GCP	Good Clinical Practice
GDPR	General Data Protection Regulation (EU) 2016/679
GSDMD	Gasdermin D
IMP	Investigational Medicinal Product
ISF	Investigator Site File (This forms part of the TMF)
ISRCTN	International Standard Randomised Controlled Trials Number
FLPI	Full-field Laser Perfusion Imaging
LPLV	Last Participant Last Visit
MA	Marketing Authorisation
MAMS	Multi-arm, multistage trials
MHRA	Medicines and Healthcare products Regulatory Agency
MMP	Matrix-metalloproteinases
NE	Neutrophil elastase
NEATstik	Neutrophil Elastase Airways Test
NETs	Neutrophil extracellular traps
NHS R&D	National Health Service Research & Development
NSP	Neutrophil serine proteases
PI	Principal Investigator
PIS	Participant Information Sheet
PWV	Pulse Wave Velocity
RSI	Reference Safety Information
QoL-B	Quality of Life Bronchiectasis
REC	Research Ethics Committee
SAE	Serious Adverse Event
SDV	Source Data Verification
SmPC	Summary of Product Characteristics
SUSAR	Suspected Unexpected Serious Adverse Reaction
TASC	Tayside Medical Science Centre
TCTU	Tayside Clinical Trials Unit
TRuST	Tayside Randomisation System
TMF	Trial Master File
TMG	Trial Management Group
TSC	Trial Steering Committee
UoD	University of Dundee
WOCBP	Women of childbearing potential

II. TRIAL SUMMARY

Trial Title	A randomised, open-label, multifactorial, multicentre, platform trial using a range of repurposed anti-inflammatory treatment to improve outcomes in patients with bronchiectasis within the EMBARC clinical research network.	
Short title	AIR-NET- Testing anti-inflammatories for the treatment of bronchiectasis	
Clinical Phase	II	
Trial Design	Randomised, open-label, multifactorial, multicentre, platform trial	
Trial Participants	Bronchiectasis patients with active neutrophilic inflammation	
Planned Sample Size	Sample size for each arm is given below.	
Treatment duration	28 days	
Follow up duration	56 days	
	Objectives	Outcome Measures
Primary	To evaluate the effect of a range of interventions compared to usual care on the activity of Neutrophil elastase in sputum	Sputum neutrophil elastase activity at day 28
Control arm	Arm 1: Usual care Participants will be contemporaneously randomised to the control arm until trial end	
Open treatment arms	Arm 2: n=42, disulfiram - two 200mg oral tablets once daily Arm 3: n=42, dipyridamole – one 200mg oral prolonged/modified release capsule twice daily Arm 4: n=42, doxycycline – one 100mg oral capsule once daily Additional treatment arms will be added as identified	
Closed treatment arms	Nil, initial trial protocol, no treatment arms have been closed.	
Sub-study		
Trial Participants	Participants recruited to the main trial at the Tayside site will be enrolled in the sub-study	
	Objectives	Outcome measures
Exploratory	To evaluate the effect of a range of interventions compared to usual care on the cardiovascular system	Pulse wave velocity Full-field Laser Perfusion Imaging

III. FUNDING AND SUPPORT IN KIND

FUNDER(S)	FINANCIAL AND NON FINANCIAL SUPPORT GIVEN
LifeArc	Funding

IV. ROLE OF TRIAL SPONSOR AND FUNDER

The roles and responsibilities of the Sponsor and Funder will be detailed in the Clinical Research Agreement.

V. ROLES AND RESPONSIBILITIES OF TRIAL MANAGEMENT COMMITTEES/GROUPS & INDIVIDUALS

The trial will be coordinated by a Trial Management Group (TMG), consisting of the grant holders, including the CI, collaborators, statistician, research assistant, trial manager and research nurse where appropriate. TMG membership details will be held in the Trial Master File (TMF). The TMG will meet regularly to ensure all practical details of the trial are progressing well and working well and everyone within the trial understands them. Minutes of the TMG meetings will be maintained in the TMF.

The trial will have an independent Trial Steering Committee (TSC). The role of the TSC will be detailed in a TSC charter and will include oversight of the conduct of the trial including decisions around stopping or adding trial arms. TSC terms of reference are detailed in the TSC Charter and held in the TMF. Minutes of the TSC will be maintained in the TMF.

A Data Monitoring Committee (DMC) will be established to oversee the safety of trial participants and will be independent of the Sponsor. The DMC will be unblinded to allocation. The DMC will meet prior to participant recruitment to decide on the frequency of DMC meetings, timings will be documented in the DMC charter. DMC terms of reference are detailed in the DMC Charter and held in the TMF. Minutes of the DMC will be maintained in the TMF.

The Chief Investigator (CI) will be responsible for the conduct of the trial. Site delegate(s) will oversee the trial and will be accountable to the CI. A trial-specific Delegation Log will be prepared for each trial site, detailing the duties of each member of staff working on the trial.

VI. PROTOCOL CONTRIBUTORS

CI: [name], review and final approval

Research Fellow: [name], initial draft, review

TCTU Senior Trial Manager: [name], initial draft, review

Senior Research Statistician: [name], review

Lead Scientist: [name], review

[figure not shown]
Clinical Trial Pharmacist: [name], review

TCTU Database Manager: [name], review

[figure not shown]
[figure not shown]
[figure not shown]
[figure not shown]
[figure not shown]
[figure not shown]
VII. KEY WORDS:

Bronchiectasis; anti-inflammatory; platform trial

VIII. PARTICIPANT FLOW CHART

IX. TRIAL TIMELINES FLOW CHART

Open/close to recruitment					New arms to be added in future	
Sept 2024	Arm 1: Usual Care  OPEN	Arm 2: Disulfiram  OPEN	Arm 3: Dipyridamole  OPEN	Arm 4: Doxycycline  OPEN		
					Arm: 5 XXX  N/A	
						Arm: 6 XXX  N/A

Dates arms closed/new arms opened will be added

1. BACKGROUND

Non-cystic bronchiectasis (hereafter referred to as bronchiectasis) is a chronic inflammatory disease with permanent bronchi dilatation, characterised by disabling productive cough, shortness of breath, and occasional haemoptysis (Barker 2002). Bronchiectasis is a heterogeneous condition that can either be a suppurative pulmonary disease on its own or overlap with other pulmonary diseases including asthma and chronic obstructive pulmonary disease ([name] et al. 2018). Data from the European Multicentre Bronchiectasis Audit and Research Collaboration (EMBARC) registry shows that approximately half of the patients with bronchiectasis experience two or more exacerbations a year, a major adverse event within the natural history of this disease. Patients who frequently exacerbate have double the mortality rate than patients who do not ([name] et al. 2014). Therefore, reducing exacerbations has now been an area of focus for most bronchiectasis research involving therapeutics.

There are few novel therapies in development for the treatment of bronchiectasis due to a lack of validated targets, and due to a lack of therapies with proof of concept to support further clinical development. The dominant mechanism of disease in bronchiectasis is chronic neutrophilic inflammation, which is near universal in patients with this condition, and which has been linked to disease severity, future exacerbations, and lung function decline. Excessive neutrophilic inflammation through the formation of neutrophil extracellular traps (NETs) is therefore a key therapeutic target in bronchiectasis ([name] et al. 2017). Dipeptidyl peptidase-1 inhibitors, which directly target neutrophilic inflammation, were recently shown to prolong time to first exacerbation in a phase 2 trial in bronchiectasis ([name] et al. 2020). Exacerbation reduction was predicted by a reduction in neutrophil elastase (NE) activity in sputum ([name] et al. 2020). NE has been shown to be a valid biomarker across multiple studies in bronchiectasis ([name] et al. 2017).

NETs and neutrophilic inflammation are therefore key therapeutic targets and validated biomarkers, which predict clinical response, with which to test the effectiveness of new therapies. Drugs which reduce neutrophil recruitment to the airway such as CXCR2 antagonists and leukotriene B4 antagonists might increase infections (Chapman et al. 2009; Döring et al. 2013; [name] et al. 2015). Therefore, anti-inflammatory treatment needs to modulate, rather than “switch off” inflammation in the airways. The cellular pathways leading to NET formation in neutrophils are now well defined and there are many potential repurposed therapies which could target this mechanism.(Döring et al. 2013; Barnes 2015).

There are no good animal models of bronchiectasis and consequently it is hard to identify candidate therapies with strong pre-clinical evidence. This means that currently, there is not one outstanding candidate for a repurposed anti-inflammatory therapy in bronchiectasis. Therefore, an approach is needed that will allow the screening of multiple drugs to identify the most effective and well-tolerated candidate for further clinical development in large scale trials.

2. RATIONALE

Understanding of the causes and consequences of bronchiectasis exacerbations has been improved recently through the latest clinical and translational research. The causes of bronchiectasis exacerbations can be broadly attributed to bacterial infection, viral infection, environmental effects, and host inflammatory response (Gao et al. 2024).

Chronic neutrophilic inflammation is a dominant part of the host inflammatory response in bronchiectasis, and has been associated with disease severity, further exacerbations, and a decline in lung function. Neutrophilic inflammation occurs partly from the accumulation of excess activity of neutrophil serine proteases (NSPs), one of which is NE. NSPs are released by neutrophils during degranulation and NETs release (NETosis) (Keir and [name] 2022). Attenuating neutrophilic inflammation was shown to reduce exacerbation frequency and prolong time to first exacerbation in the WILLOW trial, a phase 2 trial involving a novel dipeptidyl peptidase-1 inhibitor, Brensocatib ([name] et al. 2020). The WILLOW trial also demonstrated that sputum NE reduction is associated with reduction in bronchiectasis exacerbations and is a valid biomarker for other similar bronchiectasis trials.

This has promoted increasing interest around attenuating host inflammatory responses to reduce bronchiectasis exacerbations, but more research is needed around the exact mechanisms, as well as to explore wider implications.

There are numerous existing therapeutics that have shown to have secondary anti-inflammatory effects beyond their original indication (Rakocevic et al. 2023, Patel et al. 2023). Instead of repurposing and testing these therapeutics one at a time, it is proposed to establish a platform trial to enable rapid testing of multiple therapeutics within the population of bronchiectasis patients.

These repurposed therapeutics have established real-world evidence based on their safety profile, side effects, pharmacokinetics and pharmacodynamics, drug–drug interactions, and experience in different patient populations. This enables us to conduct trials more safely and cost-effectively.

In other fields such as cancer research, the idea of a randomized screening design is widely accepted (Rubinstein, 2005). In such designs, a potential treatment is tested against a control (often standard care, or an active comparator) using relaxed type I and II error rates to reduce the required sample size. This provides a pragmatic approach to quickly obtain a (non-definitive) signal of efficacy, to be confirmed in a larger phase III study, while screening out sub-optimal treatments at an early stage.

Adaptive platform trials, such as multi-arm, multistage trials (MAMS), offer the potential to expedite the testing of new therapies with reduced cost compared to conventional placebo controlled, single arm, parallel group, randomised controlled trials. Utilising repurposed compounds with established safety records in clinical practice instils greater confidence in participants and investigators, when compared to new compounds with limited long-term data or experience. MAMS have gained widespread use in the cancer field and have become more prevalent since the COVID-19 pandemic. The RECOVERY trial serves a notable example for a MAMS, using repurposed compounds such as dexamethasone, colchicine, and azithromycin among their candidates. Ultimately, the RECOVERY trial yielded the world's first effective agent against COVID-19 (Horby et al. 2020).

AIR-NET is a multi-arm, adaptive platform trial designed to test the anti-inflammatory effects of multiple repurposed compounds in patients with bronchiectasis. Participants will be randomized to one of multiple potential interventions or usual care and treated for 28-days.

The effect of treatment on sputum NE levels will be the primary efficacy outcome, and safety will be determined. The agents with the greatest evidence of target engagement and safety will be prioritised for further development. Embedded within the platform will be a programme of standardisation, capacity building and translational research that will enhance the UK's capacity to conduct early phase bronchiectasis trials.

Participants will be randomized to one of the open treatment arms they have been deemed eligible for, or usual care. Treatment will be administered for 28 days, a period which should be sufficient to demonstrate robust anti-inflammatory effects based on previous studies ([name] et al. 2020). All compounds are not currently used in the treatment of bronchiectasis as long-term therapies but have in vitro or in vivo evidence that they target neutrophilic inflammation and are widely available generic drugs which could be rapidly repurposed if shown to be effective. Any repurposed compounds demonstrating an efficacy signal against usual care will then be considered for further large-scale trials. Compounds that do not demonstrate sufficient efficacy or have safety issues will not be studied further ([name] et al. 2020). The Trial Steering Committee will evaluate the trial data to determine which compounds should be prioritised for further trials, and will review applications/proposals to add new experimental arms to the trial.

A sub-study will also be included as an option for those participants enrolled in Tayside. Neutrophilic inflammation is implicated in increased cardiovascular risk in patients with bronchiectasis and our sub-study will constitute a pilot study to determine if the interventions have an effect on biomarkers of cardiovascular risk.

Rationale for open trial treatments:

Arm 2: Disulfiram

The carbamate derivative disulfiram, a US Food & Drug Administration (FDA)-approved drug for treating alcohol dependency, received increasing research attention during the COVID-19 pandemic as both a potential anti-viral agent (Jin et al. 2020) and NET inhibitor via inhibition of Gasdermin D (GSDMD), which has shown to be involved in the generation and release of NETs (Hu et al. 2020). GSDMD cleavage and activation is the result of inflammasome activation or alternatively NE activity, which in immune cells ultimately results in active IL-1 β release from the cell, which then triggers multiple downstream immune and inflammatory processes. This includes either pyroptosis in the case of myeloid cells or NETosis in the case of neutrophils (He et al. 2015). Work within the [name] group has shown that IL-1 β and also caspase-1 activity levels in sputum from bronchiectasis patients, indicative of classical NLRP3 inflammasome activation, are associated with severe disease, mucus purulence and mucociliary dysfunction (Perea et al. 2024). In a murine model of acute lung injury, disulfiram treatment reduced NETs and lung oedema and improved survival, and in a further investigation in SARS-CoV-2 infected hamsters similar results were observed with complementary downregulation of innate immune pathways (Adrover et al. 2022). Whilst in these models total IL-1 β in the lung tissue was not reduced, other authors have shown that disulfiram does not block IL-1 β generation or impact caspase-1 dependent canonical signalling but rather prevents IL-1 β release from the cell by blocking caspase 11-dependent GSDMD pore formation. Reduced levels of IL-1 β as well as other inflammatory cytokines have been demonstrated with disulfiram treatment in pre-clinical models of LPS-induced sepsis and in human macrophages, in addition to other inflammatory cytokines including TNF and IL-6 (Hu et al. 2020). However, in murine and human macrophage cell lines in vitro in one screening study disulfiram was identified as a NLRP3 inflammasome pathway

inhibitor, and reduced ASC-speck formation implicated in classical inflammasome formation and activity (Bonnekoh et al. 2021). These processes may differ between patients and animal models utilised and may not yet be fully elucidated, however disulfiram consistently demonstrated significant beneficial effects via GSDMD inhibition. Further, disulfiram treatment was also shown to reduce histone H3 processing in neutrophils after LPS stimulation, a process concomitant with NETosis (Adrover et al. 2022). GSDMD is involved in pore-formation in neutrophil granules intracellularly, which releases NE that then acts in a positive feedback loop to activate GSDMD and promote NETosis (Sollberger et al. 2018), and reduced spontaneous NETosis when neutrophils from septic patients were treated directly with disulfiram in vitro (Silva et al. 2021). In cancer cells including malignant T-cells, disulfiram treatment has been shown to induce apoptosis and inhibit proliferation (Chen et al. 2022), these mechanisms may be cell-type specific and there is so strong evidence that apoptosis is promoted in other non-cancer cell types. On the contrary, in addition to reducing NETosis, disulfiram can act on other immune cell types to reduce harmful methods of cell death including the explosive macrophage pyroptosis. Neutrophils are not the only player in the lungs in bronchiectasis and are influenced significantly by the inflammatory environment they encounter. By impacting the proinflammatory activity of multiple cell types neutrophilic inflammation may also be quiesced.

Based on existing clinical practice, where doses of >200mg are frequently used, as well as from safety data from clinical trials, there have been no major safety concerns identified with the use of 400mg disulfiram daily. While the SmPC states that the maximum Disulfiram dose is 200mg once daily, that is in a context of a treatment duration up to six months, for patients with alcohol dependency. In the British National Formulary and clinical practice the maximum dose goes up to 500mg once daily for the treatment of alcohol dependence over a similar period, under supervision. As the recruitment cohort are not individuals with alcohol dependency, as well as excluding individuals with any major cardiovascular disease/liver/psychiatric diseases, it is thought that there are no major safety concerns about using the dose of Disulfiram 400mg once daily dose for only 28 days.

Arm 3: Dipyridamole

Adenosine triphosphate and Adenosine diphosphate released extracellularly can be detected by G-coupled receptors to activate purinergic signalling cascades in cells including neutrophils, monocytes and platelets. Neutrophils have been shown to be major P2X7R expressors, a key Adenosine triphosphate receptor, in a model of *Streptococcus pneumoniae* infection model (Karmakar et al. 2016). Downstream events after receptor engagement include NLRP3 inflammasome activation and IL-1 β production (Karmakar, et al. 2016) as well as prompting initiation of coagulation pathways promoting thrombus formation. The FDA-approved drug Dipyridamole indicated typically for thrombosis prevention, activates the A2aR adenosine receptor, and has been shown to reduce neutrophil ROS formation and NETosis (Ali, et al. 2019), whilst also having beneficial effects to reduce platelet and also endothelial activation (Chakrabarti, et al. 2005). Utilising murine models, the action of dipyridamole in neutrophils was shown to be cAMP and PKA dependent, acting to inhibit adenosine reuptake into the cell and also to stabilise cAMP by inhibiting phosphodiesterase activity which degrades cAMP to potentiate downstream effects (Ali et al. 2019, Kanthi et al. 2020). Dipyridamole has demonstrated further activities potentially beneficial in bronchiectasis. Whilst many inflammatory pathways are overactive, in other chronic lung diseases, suppressed interferon responses have demonstrated contribution to viral infection susceptibility and associated with increased exacerbation frequency

(Singanayagam, et al. 2019). Dipyridamole was shown to promote IFN signalling in murine leukocytes (Galabov and Mastikova 1982), an effect and potential mechanism warranting further investigation.

Arm 4: Doxycycline

The tetracycline derivative doxycycline is an FDA-approved antibiotic and inhibitor of extracellular matrix-degrading matrix-metalloproteinases (MMPs), with demonstrated activity against a range of MMPs shown to be increased in the airways in bronchiectasis. Amongst these are MMP-2 which has been associated with differential microbiome profiles in bronchiectasis in severe disease (Taylor et al. 2015) and MMP-9 linked with bronchiectasis progression (Garratt et al. 2015) In animal models of chronic lung disease, subsequent doxycycline treatment after disease development was able to reduce MMP-2 and -9 expression in the lungs as well as levels of the inflammatory cytokines TNF- α and IL-1 β (Hadzic et al. 2021) and neutrophil infiltration (Lee et al. n.d.). Furthermore whilst studies so far have been small and highlight the need for further investigation, a small exploratory study in patients with Chronic Obstructive Pulmonary Disease (COPD) receiving 3 months of doxycycline add-on therapy demonstrated marked reductions in MMP levels in addition to reduced markers of oxidative stress and increased antioxidant markers (Singh et al. 2019) Reduction in MMP activity with doxycycline occurs via its activity as a calcium and zinc chelator and ability to bind these ions, in addition to direct inhibition of latent pro-MMPs (Golub et al. 1998) making the measurement of MMPs a potentially attractive biomarker of drug efficacy, adherence and treatment response.

However, in a variety of immune cell types and *in vivo* models, doxycycline treatment has demonstrated anti-inflammatory effects which may be induced by a range of mechanisms, including modulation of NF κ B, Akt, MAPK and TACE activity, all of which are implicated in both acute infection and in immune dysfunction in chronic lung disease (Di Caprio et al. 2015). *In vitro*, doxycycline treatment of human peripheral blood mononuclear cells (PBMCs; consisting primarily of B and T lymphocytes) stimulated with bacterial endotoxin resulted in dose-dependent reduction in inflammatory cytokine production including IL-1 β and IL-6 (Krakauer and Buckley 2003) and monocytes stimulated with *Aggregatibacter* (Bostanci et al. 2011), and reductions at both the protein level and gene expression have been evidenced (Bode et al. 2014). Suppression of NF κ B and MAPK pathways may be responsible for this effect, and doxycycline treatment of LPS-stimulated microglial cells reduced cell activation, proinflammatory cytokine release, ROS and NO production. This study also showed that phosphorylation of p38 MAPK and also NF- κ B nuclear translocation was inhibited with doxycycline treatment (Santa-Cecilia et al. 2016). Reduction in NF- κ B activity has been demonstrated in multiple cell types after doxycycline. In cancer cells doxycycline treatment downregulated the effects of LPS stimulation of MMPs, as well as NF- κ B (Ogut et al. 2016) and this has also been demonstrated in murine macrophages (Zhang et al. 2017). In several cell lines the mechanism of action was demonstrated as reducing downstream phosphorylated I κ B- α and IKK-B levels (Alexander-Savino et al. 2016). NF κ B activation contributes to a myriad of inflammatory functions, namely increasing the production of proinflammatory proteins, in addition dysfunctional mechanisms including suppression of phagocytic processes and induction of apoptosis (Bai et al. 2019). Further upstream, as a potential mechanism of action for these effects, Doxycycline has been demonstrated to act on Nf κ B activator protein kinase C (PKC) in an *in vitro* granuloma model (Webster, Toso, and Hegemann 1994). Specific effects of doxycycline in neutrophils however have been much lesser investigated. Whilst direct application of doxycycline to

neutrophils *in vitro* has yielded mixed results, PKC and ROS activity, Akt and MAPK signalling as well as inflammasome activation have all been implicated in NETosis, and will be critical to understand whether treatment either directly or indirectly results in a reduction in NETs in the airways of patients receiving doxycycline.

In addition to reducing NFκB and MAPK activation, doxycycline has been shown to reduce NLRP3 inflammasome activation in immune cells *in vitro* and *in vivo* (Zhang et al. 2017), with similar beneficial effects to those described for disulfiram.

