6.3. Open treatment arm specific exclusion criteria

6.3.1. Arm 2: Disulfiram

- Currently on Disulfiram (patients should have a washout period of at least 30 days from last dose if they have previously received this medication)
- Hypersensitivity to Disulfiram
- Participant, or investigator objects to randomisation to Disulfiram
- Does not agree to cease consumption of alcohol during intervention and for 14 days following treatment discontinuation
- Chronic liver disease
- Alanine transaminase (ALT)>135 U/L at screening,
- Bilirubin >30 umol/L at screening.
- Uncompensated cardiac failure
- Coronary artery disease (diagnosis of stable or unstable angina, previous myocardial infarction)
- Previous history of stroke or transient ischaemic attack
- Uncontrolled hypertension
- Hereditary problems of galactose intolerance, total lactase deficiency or glucose-galactose malabsorption
- Recent psychiatric exacerbation
- Any significant acute or chronic psychiatric condition, including severe personality disorder, psychotic disorder or suicide risk.
- Hypothyroidism
- Porphyria

- Diabetes Mellitus
- Epilepsy

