6.3.3. Arm 4: Doxycycline

- Currently on Doxycycline (patients should have a washout period of at least 30 days from last dose if they have previously received this medication)
- Hypersensitivity to Doxycycline
- Participant, or investigator, objects to randomisation to Doxycycline
- Myasthenia Gravis
- Systemic Lupus Erythematosus
- Chronic Liver Disease
- Porphyria
- Alcohol dependence
- Suspected Syphilis

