7.3. Randomisation scheme

Participants will be randomised equally to any open arms they are eligible for. Participants will be allocated to an arm using a minimisation algorithm, with factors for centre, *Pseudomonas aeruginosa* infection recorded in the last 2 years and long-term use of macrolides.

Randomisation will initially open with a control arm and 3 treatment arms. When a treatment arm has recruited to its target, randomisation to that arm will be closed. When a new treatment arm is added, randomisation to that arm will be opened for all participants meeting the eligibility criteria for that arm.

Participants who have completed 56 days of follow-up (end of trial) may be rescreened and re-randomized if they are willing to participate in the trial again. Participants will receive a new copy of the current PIS, will be asked to complete a new Informed Consent Form, be given a new, unique participant identification number and eligibility will be rechecked prior to randomisation. All trial activities will be carried out as per protocol. Re-randomisation will be performed in the same way as for initial randomisations. Patients can be randomised a maximum of three times (i.e. initial randomisation and two re-randomisations).

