8. TRIAL TREATMENTS

8.1. Name, description and regulatory status of investigational medicinal products (IMPs) for open arms

	Treatment	Dosage, form and strength	Regulatory status
Arm 2	Disulfiram	400 mg oral tablets two 200mg tablets once daily	Not approved for the treatment of bronchiectasis. Has current marketing authorisation (MA) in the UK for use as an adjuvant in the treatment of drinking problems.
Arm 3	Dipyridamole	200mg oral prolonged/modified release capsule one capsule twice daily	Not approved for the treatment of bronchiectasis. Has current MA in the UK for use in secondary prevention of ischaemic stroke and transient ischaemic attacks and as an adjunct to oral anti-coagulation for prophylaxis of thromboembolism associated with prosthetic heart valves.
Arm 4:	Doxycycline	100mg oral capsule one capsule once daily	Not approved for the treatment of bronchiectasis. Has current MA in the UK for use in the treatment of a variety of infections caused by susceptible strains of Gram-positive and Gram-negative bacteria and certain other micro-organisms.

8.2. Name, description and regulatory status of IMP(s) for closed arms.

Nil, initial trial protocol, no treatment arms have been closed.

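### The disulfiram 400 mg dose rests partly on a cohort without alcohol dependence, but no eligibility criterion for that arm secures this

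*Protocol*

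**What the plan says.** The dose argument is in section 2, under Arm 2. It acknowledges the licensed limit ("While the SmPC states that the maximum Disulfiram dose is 200mg once daily") and adds that in the British National Formulary and in practice "the maximum dose goes up to 500mg once daily for the treatment of alcohol dependence over a similar period, under supervision". It then concludes that 400 mg for 28 days raises no major safety concern. Two statements about who will be enrolled support that conclusion. One is "As the recruitment cohort are not individuals with alcohol dependency". The other is that people with major cardiovascular, liver or psychiatric disease are excluded.

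The disulfiram exclusions are in section 6.3.1. The only item about alcohol is "Does not agree to cease consumption of alcohol during intervention and for 14 days following treatment discontinuation". Previous disulfiram users may enter after an interval: "patients should have a washout period of at least 30 days from last dose if they have previously received this medication". Section 8.1 gives the drug's UK authorisation as "for use as an adjuvant in the treatment of drinking problems".

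Section 6.3.3, for doxycycline, lists "Alcohol dependence" as an exclusion in its own right. Neither the inclusion criteria (6.1) nor the general exclusions (6.2) mention it.

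**The concern.** A dose above the licensed maximum is defended by a description of the participants, and the eligibility criteria should make that description true. For the cardiovascular, liver and psychiatric part they do, with named items in 6.3.1. For alcohol dependence they do not.

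The issue is safety. Section 2.1 says the reaction between disulfiram and alcohol can be severe and life-threatening. Appendix 1 says its severity is related to the disulfiram dose and the alcohol intake, and that it has been seen at blood alcohol as low as 10 mg/100 ml. The formulary dose range cited for dependent patients is a supervised one. In the trial, drug is dispensed at day 0 (Appendix 4), and adherence is checked by asking at each visit and by a tablet count at the last visit (8.12). A currently dependent drinker may find an agreement to abstain hard to keep, and the dose rationale assumes that no such person is present.

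**Working it through.** The documents state no figure to reproduce. The check compares the rationale with the criteria.

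**1. Where the dose sits (section 2).**
- Against the SmPC maximum: 400 / 200 = 2.0.
- Against the formulary maximum for supervised treatment of dependence: 400 / 500 = 0.8.

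The dose is off label on the first comparison and within the cited range on the second.

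**2. Premises about the cohort, and the criteria that secure them.**

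| Premise in section 2 | Criterion applying to the disulfiram arm |
|---|---|
| Major cardiovascular disease excluded | 6.3.1: uncompensated cardiac failure, coronary artery disease, stroke or TIA, uncontrolled hypertension |
| Liver disease excluded | 6.3.1: chronic liver disease, ALT above 135 U/L, bilirubin above 30 umol/L |
| Psychiatric disease excluded | 6.3.1: recent exacerbation, any significant acute or chronic condition |
| Not alcohol dependent | None in 6.1, 6.2 or 6.3.1 |

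**3. Whether another criterion already covers dependence.**
- *Agreement to abstain (6.3.1, 8.11).* This tests willingness. A dependent person who agrees passes.
- *Capable of complying with trial procedures (6.1).* This could exclude such a person, at the investigator's discretion.
- *Liver criteria (6.3.1).* These catch dependence only when it has produced liver disease or raised tests. Section 6.3.3 also excludes chronic liver disease and still lists alcohol dependence separately, so the protocol does not treat one as covering the other.
- *Psychiatric criterion (6.3.1).* An investigator could class dependence here, but the examples given do not include it.
- *Investigator objection (6.3.1).* Available, and again discretionary.

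Each can exclude a dependent person; none must. Section 13.5 allows no waivers, so the written criteria decide who enters.

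**4. Effect on allocation.** Section 7.3 says "Participants will be randomised equally to any open arms they are eligible for". With all four arms open, a person eligible for every arm has a 1/4 = 25% chance of disulfiram. A dependent person barred only from doxycycline has 1/3 = 33%. This ignores minimisation and assumes that no other arm is barred and that all arms are available at the site. With the criterion added, the chance is zero, and usual care and dipyridamole remain open to that person.

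**The case against.** The case for leaving the text alone has real strength.

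- **The premise does not carry the dose by itself.** Section 2 also relies on clinical practice above 200 mg, trial safety data, the 500 mg formulary maximum, the other exclusions and the short treatment. This stands. A reader might infer that the justification for 400 mg collapses without the premise; the text does not support that.
- **The sentence may only mean that people are recruited for bronchiectasis.** That is a possible reading. However, the sentence is used as a safety ground, bronchiectasis does not rule out dependence, and 6.3.3 shows that the authors foresaw such patients.
- **The agreement to abstain is not the only protection.** Correct. Besides the filters above, participants receive written advice on avoiding products containing alcohol (8.11). Liver tests are done at screening and at days 14, 28 and 56 (Appendix 4). The DMC reviews safety and compliance once the tenth participant in the arm reaches day 28 (10.4). The later checks limit harm after entry but do not decide eligibility.
- **Dependence would probably be noticed at screening.** Medical history covers conditions tied to the criteria (7.7), which include dependence through 6.3.3, and eligibility is assessed arm by arm (7.3.1). This also stands. It means that the information will be at hand, but no disulfiram criterion tells the investigator to act on it.
- **The washout line proves little.** A reader might take it as evidence that dependent drinkers are expected, given the licensed use. The same wording appears for all three drugs, it concerns earlier exposure, and a former user need not be dependent now.

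**Conclusion.** The inconsistency holds in a limited form. Section 2 uses the absence of alcohol dependence as one of several grounds for a dose at twice the cited SmPC maximum, and no criterion in 6.1, 6.2 or 6.3.1 secures it. The remaining gap is a currently dependent person who agrees to abstain, passes the liver and psychiatric criteria, is judged able to comply and draws no objection from the investigator.

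How many participants that describes cannot be said. The documents give no prevalence, and a figure for expected cases among the 42 in the arm would rest wholly on an assumed rate. Nor do the documents support barring everyone with past dependence or past disulfiram treatment: the rationale speaks of people who are dependent, and a long-abstinent person is a different case. The point concerns eligibility and safety; the estimand, power, error rate and analysis are unaffected. It is worth correcting because the consequence of a breach can be serious and the correction is small.

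**What to change.** Add "Alcohol dependence" to the disulfiram exclusions in section 6.3.1, in the same words as 6.3.3, so that the criteria secure what section 2 assumes. The washout line can stay, and long-abstinent people need not be excluded.

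The change is one line in a protocol amendment. Screening already has to establish the fact for doxycycline, and eligibility is already recorded for each arm, so no new assessment is needed. The downside is that a few patients become ineligible for disulfiram; they can still be randomised among the other arms for which they qualify. The target of 42 and the analysis stay as they are.
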